4.4 Per patients sensitivity and specificity (secondary endpoint)

Based on feedback from FDA, Lumicell is including an analysis of sensitivity and specificity at the patient level. Because a single patient can have up to 6 lumpectomy cavity orientations, each orientation with its own image, there will be patients that can have truth standard negatives and truth standard positives within the cavity. Thus, we propose to evaluate the per-patient truth standards as described below.

LUMICELL CONFIDENTIAL

This document is confidential. Do not disclose or use except as authorized.

Definitions for per-patient truth standards:

- Truth standard positive patient: a patient having at least one orientation as a truth standard positive using the per-tissue hierarchical approach
- Truth standard negative patient: a patient having all orientations as truth standard negatives using the per-tissue hierarchical approach.

Definitions for per-patient Lumicell imaging results:

- Positive detection patient by Lumicell imaging device: Lumicell device detects at least one positive signal in a patient
- Negative detection patient by Lumicell imaging device: Lumicell device does not detect any positive signal in a patient; that is, all Lumicell signals for that patient are negative.

Using these definitions, the per-patient 2x2 contingency table will be populated as:

- True positives: truth standard positive patients with positive detection by Lumicell imaging device
- True negatives: truth standard negative patients with negative detection by Lumicell imaging device
- False negatives: truth standard positive patients with negative detection by Lumicell imaging device
- False positives: truth standard negative patients with positive detection by Lumicell imaging device

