5.2.8 Lumicell procedure (only patients randomized to the intervention arm)

After the standard of care is completed for patients randomized “to proceed” with the Lumicell intervention, the surgeon will scan the tumor bed to collect images of the cavity walls and remove therapeutic shaves as indicated by the LUM decision software (refer to the Instructions For Use manual for details). The software will automatically turn on the tumor detection algorithm to allow visualization and navigation of the lumpectomy cavity with highlighting of suspected tumor by the tumor detection algorithm.

5.2.8.1 When there is no tissue available to be removed from a given orientation (e.g., too close to skin or too close to the chest wall), no LUM image shall be collected from that orientation. This information must be documented.

5.2.8.2 The surgeon shall scan the cavity and generate images from each orientation. Images should be generated and saved for both LUM positive and negative results.

5.2.8.3 The surgeon shall take a Lumicell shave from each imaged location indicated as “positive” by the LUM decision software.

5.2.8.4 A maximum of two (2) Lumicell shaves may be taken from any one orientation. Additional Lumicell shaves beyond 2 per orientation will constitute a protocol violation.

5.2.8.5 The resected tissue(s) shall be handled and named according to the Appendix B.

If a shave is not taken when indicated by the LUM Imaging System or a Lumicell image is not recorded as described above, a protocol deviation will be recorded with exception as described in section 5.3.1. If images are not saved in all orientations, a protocol deviation will be recorded unless there is no enough tissue left to take a shave (see 5.2.8.1). The reason for not taking a shave when indicated by the Lumicell system shall be recorded.

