3.2 Three co-primary endpoints

3.2.1 Removal of residual cancer

Ratio of patients who have **residual cancer** found in at least one LUM-guided shave (also known as therapeutic shave or “T-shaves”) among all patients randomized to the device arm. **Residual cancer** is defined as tumor found by pathology in a therapeutic shave after the SOC surgical procedure is completed; that is, tumor that current SOC surgery failed to remove (Figure 1). Mathematically, it is defined as:

$$\frac{\# \text{ patients with residual cancer found in at least one therapeutic shave}}{\text{Total number of patients}}$$

[figure not shown]

Figure 1: Depiction of primary endpoint

[figure not shown]
This proposed primary endpoint for determination of whether tumor is found in at least one therapeutic shave, the **ground truth** of histopathology assessment of the therapeutic shave is used.

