3.2.2 Sensitivity and specificity

The instrument diagnostic accuracy is measured by sensitivity and specificity on a per-tissue basis. Because a LUM-guided shave does not exist when a negative LUM image is indicated we propose a hierarchical approach to determine the truth standard as depicted in Figure 2. The highest truth standard is whether pathology finds cancer in a tissue shave removed from the area that was imaged in the cavity. When a shave does not exist, then whether tumor is found in a re-excision surgery is considered as the truth standard. When neither a shave nor a second surgery exists for a given orientation that was imaged, the margin assessment of that orientation is used as truth standard. We believe that the hierarchical approach outlined to determine the truth standard is the most meaningful and practical assessment of device accuracy to predict the presence of cancer in the cavity.

LUMICELL CONFIDENTIAL

This document is confidential. Do not disclose or use except as authorized.

True positive = truth standard positive & Lum cavity image positive
 False negative = truth standard positive & Lum cavity image negative
 True negative = truth standard negative & Lum cavity image negative
 False positive = truth standard negative & Lum cavity image positive

Figure 2: Definition of truth standard to evaluate the LUM Imaging System diagnostic performance.

When a therapeutic shave and re-excision are not available for a given orientation, the margin from the prior resected tissue of the corresponding orientation will be used as ground inferred truth for evaluation (Figure 3). The number of prior positive margins contributing to the ground inferred truth for a patient will not exceed the number of orientations with positive margins.

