3.3 Secondary endpoints

- a. Proportion of patients with positive margins after standard of care breast-conserving surgery who have a LUM Imaging System signal in the cavity above the threshold as defined by the tumor detection algorithm (i.e., a positive LUM signal). The endpoint is mathematically defined as:

$$\frac{\# \text{ positive margin patients after SOC with LUM signal above the threshold}}{\# \text{ positive margin patients after SOC}}$$

If a subject has more than one orientation with an SOC positive margin, LUM imaging must correctly identify all orientations with an SOC positive margin for success of this endpoint.

- b. Proportion of subjects with pathology-positive margins after standard of care breast-conserving surgery for whom additional LUM Imaging System-guided shaves resulted in pathology-negative margins. Note: This endpoint also estimates the potential reduction in re-excision surgeries following standard of care breast-conserving surgery that resulted from a positive SOC margin. This is estimated as:

$$\frac{\# \text{ positive margin patients after SOC with all final negative margins after the LUM procedure}}{\# \text{ positive margin patients after SOC}}$$

- c. Proportion of subjects with pathology-positive margins after standard of care breast-conserving surgery for whom additional LUM Imaging System-guided shaves resulted in pathology-negative margins among all patients. This is estimated as:

$$\frac{\# \text{ positive margin patients after SOC with all final negative margins after the LUM procedure}}{\text{Total number patients}}$$

- d. Ratio of patients with negative margins after the SOC procedure who have residual cancer found in at least one Lumicell-guided (or therapeutic) shave among patients with negative margins. This is estimated as:

$$\frac{\# \text{ negative margin patients after SOC with residual cancer found in at least one therapeutic shave}}{\# \text{ negative margin patients after SOC}}$$

- e. Ratio of patients with negative margins after the SOC procedure who have residual cancer found in at least one Lumicell-guided (or therapeutic) shave among all patients

$$\frac{\# \text{ negative margin patients after SOC with residual cancer found in at least one therapeutic shave}}{\text{Total number of patients}}$$

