4.11 General considerations

All analyses will be performed under Good Clinical Practice (GCP) standards using a prespecified statistical analysis plan (SAP). Analyses will be conducted and tables and listings generated using Statistical Analysis System (SAS®) Version 9.4 or higher. Graphics may be prepared with SAS Version 9.4 or higher; R version 3.6.1 or higher, SigmaPlot 12.3 or higher. Subject level data will be provided as a listing to support tables and figures. Summaries will be provided overall, by SOC surgery type (lumpectomy/selective vs comprehensive), and by site.

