4.11.3 Missing and spurious data

During LUM-guided imaging, when there is not enough tissue to be removed (e.g. too close to skin or too close to the chest wall) no LUM image shall be recorded because it does not generate an actionable result.

In the case where the LUM Imaging System indicates that a therapeutic shave needs to be removed but the surgeon decides not to follow this guidance, the reason for not doing so will be recorded in the patient's CRF or during imaging. These instances are considered as a protocol deviation. There are other cases when the LUM-guide shave reach the protocol limit of 2 guided shaves per orientation, so a third guided shave will not be performed. In these cases, the data will be included in the performance evaluation as is; that is, because these will not generate a LUM-guided shave they will not be evaluated as removing cancer or converting positive margins to negative margins. However, they will be evaluated for the per-tissue sensitivity and specificity calculation according the hierarchical approach described in section 3.2.2.

In occasions, a cavity image may be recorded from an unintended region or the image may be deemed as low quality (blurry, out of focus, etc.). For example, the surgeon realizes that he/she placed the device in the wrong location within the cavity after recording an image. Since the LUM software does not allow to overwrite saved images, the error images will be labeled as "image error delete", and the image will be excluded from the analysis.

Other specific cases will be handled as described below.

- a. When a patient was prescribed Letrozole adjuvant therapy prior to surgery, the patient will be removed from the device performance evaluation (major protocol deviation) in the per-protocol analysis but will be included in the mITT population for primary analysis.
- b. When the time from injection of LUM015 to initial imaging time is greater than 6 hours due to unplanned surgical delays, the patients will be removed from the device performance evaluation (major protocol deviation) in the per-protocol analysis but will be included in the mITT population for primary analysis.
- c. For the re-excision rate endpoints, all patients undergoing a re-excision will be included in the analysis.
- d. In the case of a therapeutic shave taken but no image saved before the shave was removed, the shave will be excluded from analysis but will be included in the estimation of final margin.

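### Per-patient sensitivity in SAP 4.4 credits a LUM signal anywhere in the cavity, so it cannot be read as the share of patients whose cancer was located

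*SAP*

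**What the plan says.** SAP 4.4 adds a patient-level analysis of sensitivity and specificity in response to FDA feedback. A patient is truth-positive if at least one orientation is truth-positive under the per-tissue hierarchy. The device result is also any-orientation: "Positive detection patient by Lumicell imaging device: Lumicell device detects at least one positive signal in a patient". The table then counts "True positives: truth standard positive patients with positive detection by Lumicell imaging device". Nothing requires the signal and the cancer to be in the same orientation, although the section itself notes that one cavity can hold both truth-positive and truth-negative orientations.

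Elsewhere the plan works by location:

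- SAP 3.2.2, per tissue: "False negative = truth standard positive & Lum cavity image negative".
- Protocol 5.2.8.3: "The surgeon shall take a Lumicell shave from each imaged location indicated as" positive by the software.
- SAP 3.3, endpoint a, in patients with positive standard-of-care (SOC) margins: "LUM imaging must correctly identify all orientations with an SOC positive margin for success of this endpoint".

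**The concern.** The device exists to direct excision to a place in the cavity. Take a patient with cancer in one wall that the device missed and a false signal on another wall. Per tissue she contributes a false negative and a false positive. In the SAP 4.4 table she is a true positive.

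A result labelled per-patient sensitivity and prepared for a regulator may well be read as the share of patients whose cancer the device found. Part of it may be signals that led the surgeon elsewhere. The effect on sensitivity has one direction only, and its size depends on how often false signals occur.

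**Working it through.** **The plan's own figure.** SAP 4.4 gives no expected value, goal or power. The nearest stated figure is the Protocol 15.3.2 power for per-tissue sensitivity: 70 events, 40% against 60%, exact binomial, one-sided 2.5%. Rejecting at 37 or more gives size 0.020 and power 0.909, in line with the stated 90%.

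**Identity.** Among truth-positive patients:

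any-signal sensitivity = P(signal on at least one positive orientation) + P(no signal on a positive orientation, at least one on a negative orientation).

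The first term is the location-matched figure. The second is the gap, which cannot be negative.

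**Inputs.**

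- Per-tissue sensitivity s: 0.60 (planning value) and 0.69 (Phase C), SAP 4.3.2.
- False-signal rate f: 0.30 to 0.35, from specificity of 70% (Phase C) and 65% (planning).
- A lower f from the 1.1 guided shaves per patient in Phase C, treating each shave as one false signal: 1.1/6.7 = 0.164 to 1.1/6 = 0.183. The 6.7 is 1021/152 truth-negative tissues per patient (SAP 4.5). For comparison, 0.30 × 6.7 = 2.0 signals per patient, well above 1.1.
- ICC: 0, 0.145 and 0.22 (the last two from SAP 4.3.2).
- Assumed, not in the documents: six orientations, m positive and k = 6 − m negative.

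**Formula.** Under independence, matched = 1 − (1 − s)^m and any-signal = 1 − (1 − s)^m (1 − f)^k. For correlation, the no-signal probabilities were replaced by beta-binomial zero terms within the positive and the negative group, or by a latent normal patient effect shared by both groups.

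**Examples at s = 0.60, f = 0.35.**

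- m = 1, independence: 1 − 0.40 × 0.65^5 = 0.954 against 0.60 matched. With ICC 0.22: 0.901 (beta-binomial) or 0.843 (shared effect).
- m = 2, independence: 1 − 0.16 × 0.65^4 = 0.971 against 0.840. With ICC 0.22 (beta-binomial): 0.937 against 0.787.
- m = 1, s set to zero: 1 − 0.65^5 = 0.884, or 0.752 with ICC 0.22. A device that never signals on cancer would still score 75% to 88%.

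**Gap in percentage points over all models.**

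| Positive / negative orientations | f = 0.30–0.35 | f = 0.164–0.183 |
|---|---|---|
| 1 / 5 | 15–35 | 7–25 |
| 2 / 4 | 5–15 | 2–9 |
| 3 / 3 | 1.5–8 | 0.5–5 |

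**Which row is likelier.** Scaling the planned events to Phase C gives 70/268 × 230 = 60 events; 60 × 0.69 = 41 true-positive tissues. Spread over the 26 patients with cancer in a guided shave, that is 41/26 = 1.6 per patient. This is only suggestive, but it points away from the first row.

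**Can other outputs recover the split?** The first co-primary numerator is "patients with residual cancer found in at least one therapeutic shave". Subtracting it from the SAP 4.4 true positives gives an approximate upper bound on the off-site-only count. It is not the count itself: a signal on a truth-positive orientation may produce no guided shave, because guidance was declined or the limit of two shaves was reached. SAP 4.11.3 says of such cases, "because these will not generate a LUM-guided shave they will not be evaluated as removing cancer". In 268 patients the numerator is 0.09 × 268 = 24 to 26/230 × 268 = 30.

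- 70 truth-positive patients (m = 1): any-signal true positives 49.2 to 67.5, so a bound of 19 to 43, against 5 to 25 truly off-site only.
- 35 truth-positive patients (m = 2), keeping only cases where the matched count is at least the numerator: 28.2 to 34.4, so a bound of 1 to 10, against 1 to 5.

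Endpoint a matches by orientation but covers only patients with positive SOC margins.

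**The case against.** The strongest reply is that nothing here is in error. An any-against-any patient table is openly defined, internally consistent and may be what FDA asked for. Location is already handled by the tested co-primary endpoints: per-tissue sensitivity and specificity, and cancer in a guided shave. The same false signals pull down per-patient specificity in the same table, to about 8% (independence) or 21% (ICC 0.22) with six truth-negative orientations at 65% per-tissue specificity, which warns against reading the sensitivity alone. SAP 4.11 also plans listings ("Subject level data will be provided as a listing to support tables and figures"), so the split could be worked out.

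The large gaps can be attacked as well. With one positive orientation per patient, 70 × 0.60 = 42 or 70 × 0.69 = 48 patients would have an on-site signal, against 24 or 30 with cancer in a guided shave. Either pairing leaves about 18 unexplained, more than declined guidance or the shave limit would plausibly produce. And 6.7 truth-negative tissues per patient does not fit a six-orientation model exactly.

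Much of this stands. There is no contradiction, the co-primary results are untouched, and the top of the range is the less likely end. It does not remove the point. Per-tissue sensitivity counts tissues, not patients. Per-patient specificity describes truth-negative patients and does not show how many truth-positive patients were counted on off-site signals alone. A split that can be derived by hand from listings is not a planned result.

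**Conclusion.** The concern holds. Per-patient sensitivity as defined measures whether the device signalled anywhere in a patient with residual cancer, not whether it signalled where the cancer was. That follows from the definitions and needs no model.

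The size is unknown. Under the assumptions above the gap is about 2 to 35 points with one or two positive orientations per truth-positive patient, and 0.5 to 8 with three. Two positive orientations with the shave-based false-signal rate give 2 to 9 points, and the Phase C hint makes the top of the range the less likely end. These figures rest on six orientations, on per-tissue rates carrying over to orientations, and on the correlation models used.

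The consequence is confined to a secondary endpoint with no performance goal. It should be corrected because it changes what that endpoint can be taken to show.

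**What to change.** Keep the SAP 4.4 definition and 2×2 table, and label the result *any signal in the cavity*. Beside it, report:

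1. the proportion of truth-positive patients with a LUM-positive result in at least one truth-positive orientation;
2. the number of truth-positive patients whose only signals were in truth-negative orientations.

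State that (1) can still include a patient with another positive orientation missed. Do not combine (1) with the any-signal specificity in one 2×2 table or Youden Index, since the two use different rules for a positive result.

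The SAP, dated 17NOV2021, already cites 406 enrolled patients. The addition should be specified before the endpoint is computed, or be labelled post hoc.

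The cost is one label and one extra table from orientation-level results the co-primary analysis already requires. The downside for the sponsor is that a per-patient sensitivity equal to or less favourable than the planned one appears next to it.

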4.5 Study sample size, event-driven design, and overall study power

The pivotal study is powered based upon targeting success for the three co-primary endpoints as outlined above. The efficacy endpoints will be assessed in the patients who undergo LUM-guided imaging (not the 1/10th of subjects randomized to the control arm).

Based on Phase C data, it is expected that 268 patients will provide the necessary 70 truth standard positive events to power for sensitivity. Also, based on Phase C data, it is expected that 152 patients will provide the necessary 1021 truth standard negative events to power for specificity. To power for the removal of residual cancer endpoint, approximately 220 patients are required. Thus, the size of this study is driven by the necessary number of truth standard positive events.

Adding 15% to the sample size of 268 patients to include subjects in the control arm and some expected data loss, it is estimated that 310 total patients will be needed for the pivotal study. However, given the uncertainty of translating the number of truth standard positive events to actual number of patients, the pivotal trial is planned as event-driven clinical study. Patients will be enrolled until 70 truth standard positive events are reported, up to a maximum of 450 patients. The number of truth standard positive events will be counted based on the truth standard hierarchical approach from Figure 2. Counting of these events will be conducted via software programming to read from the electronic data capture system; no endpoints will be calculated at that time. Results from the event counting process will be accessible to the DSMB which will then inform Lumicell

LUMICELL CONFIDENTIAL

This document is confidential. Do not disclose or use except as authorized.

personnel on whether the targeted number of events has been reached or if enrollment needs to continue.

With the proposed sample size from sensitivity, under the alternative hypothesis for specificity using the GEE model with a compound symmetry correlation structure, the power to show true specificity above the performance goal of > 60% will be >99%. For removal of residual cancer, the power is estimated at 96%. Thus, the overall study power is $90\% \times 99\% \times 96\% = 86\%$.

4.6 Overall primary hypotheses

The overall primary hypotheses for the primary endpoint is

$$H_0^p \text{ (null): } H_0 \text{ or } H_{01}^s \text{ or } H_{02}^s \text{ versus } H_1^p \text{ (alternative): } H_1 \text{ and } H_{11}^s \text{ and } H_{12}^s$$

The removal of residual cancer, sensitivity and specificity will be tested at a one-sided significance level of 2.5%.

4.7 Methods for additional analyses

Secondary outcomes involving proportions will be analyzed using methods for Binomial distributions akin to the ones described above. Continuous measurement will be summarized using means and standard deviation and 95% confidence intervals. The percent of people with a specific AE will be reported in prespecified groups. The percent of subjects with adverse events in subjects that have at least one therapeutic shave will be compared with the percent of subjects with adverse events that have no therapeutic shaves using Fisher's exact test or goodness of fit test.

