8 INTERVENTIONAL PLAN

8.1 LUM015 administration

The investigational imaging agent LUM015 will be administered at the surgical center or hospital 4 ± 2 hours prior to the first image recorded. See section 9 for more details about the preparation and administration of LUM015.

No investigational or commercial agents or therapies other than those described in this protocol may be administered with the intent to image the subject's malignancy intraoperatively.

As per IV injection standard of care, all subjects will be observed for signs of extravasation, or allergic reaction following administration of LUM015 to monitor for adverse pharmacological activity related to the investigational agent. If extravasation is suspected or confirmed, the injection

LUMICELL CONFIDENTIAL

This document is confidential. Do not disclose or use except as authorized.

must be stopped immediately and reported to Lumicell. All study safety assessments will continue until the first post-operative visit (approximately 2-3 weeks after surgery).

If there is evidence supporting that extravasation of LUM015 injection occurred, then that patient will be excluded from the efficacy cohort. However, the patient will be included in the safety data analysis.

If the patient is experiencing an allergic reaction to LUM015 administration, the injection should be stopped immediately, and the following lab values should be obtained:

- Histamine
- Total Blood Complement
- Tryptase levels

The blood draw for each of these tests should be done as soon as possible after the start of the reaction and again at 30 minutes post start of the reaction. If an immediate blood draw is not possible, collect a 30-minute blood draw at minimum. Each blood specimen should be processed, packaged and shipped to the contracted central laboratory for this study. Specific instructions on collection, processing, and shipping can be found in the training materials associated with this study.

In case of an allergic reaction to LUM015, sites should not discard any residual drug remaining in the used syringe. This drug should be stored at -20 degrees C until a Lumicell representative notifies your site of how to proceed with the used syringe. If this process conflicts with site specific SOPs, the clinical site should notify Lumicell in advance of study start that residual drug will not be able to be maintained.

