11.2 Expected adverse events (associated with LUM015)

During Phase C of the Feasibility Study, one patient had an anaphylactic reaction to the LUM015 injection. This patient had a history of allergic reactions to contrast agents. The event was resolved within 24 hours of occurrence. We now consider anaphylactic reaction an expected adverse event, with occasional occurrence and serious severity. Table 4 below lists the expected adverse events due to LUM015 injection with their estimated occurrence and severity.

Table 4: List of expected adverse events due to LUM015 administration.

Adverse Events (Drug Related):	Occurrence:	Severity:
LUM015 extravasation	Occasional	Minor
Chromaturia	Frequent	Negligible
Anaphylaxis/hypersensitivity	Occasional	Serious

No adverse events related to the administration of LUM015 were observed during the Phase 1 IND safety study. Temporary blue/green discoloration of the urine was noted in these patients due to the blue color of LUM015. Prior to the Phase 1 study, LUM015 had not previously been used in humans. Lumicell's preclinical studies demonstrated that it was reasonably safe to proceed with a Phase 1 IND study in humans. Preclinical studies in rats showed no LUM015 related effects on clinical observations, FOB evaluation, body weights, food consumption, ocular condition, clinical chemistry, hematology and coagulation parameters or organ weight at doses up to 53-fold higher than in humans.

The results from the repeat dose toxicity study in dogs (performed by NCI) show that administration of 0.5 or 10.0 mg/kg of LUM015 intravenously once daily for seven consecutive days (8 total doses) did not cause any observable target organ toxicities. The only observable effect was hypersensitivity in several dogs.

The results from a repeat dose toxicity study in rabbits show that administration of 15 mg/kg of LUM015 intravenously one daily for seven consecutive days was well tolerated. The test article-related findings were limited to transient blue/green discoloration of the urine. There were no test article-related adverse events observed and no hypersensitivity was seen.

Additional information is available in the Investigator's Brochure for LUM015.

Clinicians should be prepared for a possible hypersensitivity or allergic reaction to occur during each administration of LUM015. Standing orders should be in place in the event of a hypersensitivity or allergic reaction for immediate intervention including administration of

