12 ADVERSE EVENT REPORTING REQUIREMENTS

12.1 Definitions

12.1.1 Adverse Event (AE)

An adverse event (AE) is any undesirable sign, symptom or medical condition or experience that develops or worsens in severity after starting the first dose of study treatment or any procedure specified in the protocol, even if the event is not considered to be related to the study. The severity of any possible AE observed will be classified per the grading established by the Common Terminology Criteria for Adverse Events (CTCAE) 5.0.

Abnormal laboratory values or diagnostic test results constitute adverse events only if they induce clinical signs or symptoms or require treatment or further diagnostic tests.

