12.8 Monitoring of adverse events/adverse device effects and period of observation

All adverse events and adverse device effects, both serious and non-serious, and deaths that are encountered from initiation of study intervention and throughout the study, should be followed to

LUMICELL CONFIDENTIAL

This document is confidential. Do not disclose or use except as authorized.

their resolution, or until the principal investigator assesses them as stable, or the principal investigator determines the event to be irreversible, or the subject is lost to follow-up. The presence and resolution of AEs, ADEs, SAEs and UADEs (with dates) should be documented on the appropriate case report form and recorded in the subject's medical record to facilitate source data verification.

For some SAEs/UADEs, the investigator, Sponsor, or designee may follow-up by telephone, fax, and/or monitoring visit to obtain additional case details deemed necessary to appropriately evaluate the SAE/UADE report (e.g., hospital discharge summary, consultant report, or autopsy report).

Subjects should be instructed to report any serious post-study event(s) that might reasonably be related to participation in this study. The principal investigator should notify Lumicell and the IRB of any unanticipated death or adverse event occurring after a subject has discontinued or terminated study participation that may reasonably be related to the study.

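### The AE comparison by therapeutic shave counts every AE from the LUM015 injection onward, so injection effects that a shave cannot cause dilute any shave-related excess by an amount the documents do not fix

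*SAP*

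**What the plan says.** SAP 4.7 states: "The percent of subjects with adverse events in subjects that have at least one therapeutic shave will be compared" with the percentage in subjects without a therapeutic shave. The test is Fisher's "exact test or goodness of fit test". SAP 4.8, SAP secondary endpoint x and protocol secondary endpoint h repeat the comparison. None of the four limits it by onset time, relatedness or type of event.

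Protocol 12.1.1 defines an AE as an undesirable sign, symptom or condition that "develops or worsens in severity after starting the first dose of study treatment or any procedure specified in the protocol", whether or not it is thought related to the study. Protocol 12.8 likewise covers events "encountered from initiation of study intervention and throughout the study".

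On timing, protocol 5.1 and 5.2.3 have all eligible subjects injected with LUM015 4 ± 2 hours before the first image. Under 5.2.7 and 5.2.8, therapeutic shaves follow only after standard of care (SOC) is complete and the allocation has been revealed.

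Protocol 11.2 says that Table 4 "lists the expected adverse events due to LUM015 injection with their estimated occurrence and severity". It has three entries: chromaturia (Frequent, Negligible), extravasation (Occasional, Minor) and anaphylaxis/hypersensitivity (Occasional, Serious). It gives no percentages.

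**The concern.** The documents do not state the purpose of this comparison, but its natural use is to show whether the extra resection adds harm. As written, a subject whose only event is blue-green urine counts the same as a subject with a cavity infection or hematoma. Injection effects arise in both shave groups and raise both percentages, which pulls them together.

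A second mechanism has a direction. Protocol 8.1 says: "If the patient is experiencing an allergic reaction to LUM015 administration, the injection should be stopped immediately". A subject whose reaction prevents guided resection has still received LUM015. She therefore stays in the safety population and enters the no-shave group with an AE. That raises the comparator rate and makes shaves look safer.

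At stake is how a non-significant result is read. If background events are common, it says little about harm from the shaves.

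**Working it through.** The documents give no AE rate, power or sample size for this comparison, so there is no stated figure to reproduce. What follows is an illustration.

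**Inputs**
- Safety N = 406 (SAP 1.1).
- Split of 200 shaved and 206 not shaved: assumed. The documents give only a Phase C average of 1.1 additional shaves.
- AE risk apart from injection effects: 20% with a shave, 10% without (assumed).
- b, the probability of a recorded injection-related AE: unknown, taken as equal in both groups and independent of other AEs.
- Two-sided 5% level: assumed, since SAP 4.7 states none for this test.

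**Formula.** P(any AE) = 1 − (1−b)(1−s), where s is the risk apart from injection effects. The observed difference is therefore (1−b)(s₁ − s₀). For b = 0.5: 1 − 0.5×0.8 = 60% against 1 − 0.5×0.9 = 55%, so a 10-point excess becomes 5 points.

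**Power by exact enumeration of Fisher's test**

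| b | Shave | No shave | Difference (points) | Power |
|---|---|---|---|---|
| 0% | 20.0% | 10.0% | 10.0 | 79% |
| 2% | 21.6% | 11.8% | 9.8 | 74% |
| 5% | 24.0% | 14.5% | 9.5 | 67% |
| 10% | 28.0% | 19.0% | 9.0 | 55% |
| 20% | 36.0% | 28.0% | 8.0 | 38% |
| 50% | 60.0% | 55.0% | 5.0 | 16% |
| 80% | 84.0% | 82.0% | 2.0 | 7% |

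**Other assumed inputs.** Take 15% vs 5%, with 60% of about 369 device-arm subjects having a shave (221 vs 185). Power is then 92% at b = 0, 86% at 2%, 61% at 10%, 29% at 30% and 16% at 50%. With a shave share of 40% or 80%, power at b = 30% is 27% or 23%. The pattern does not depend on one choice of inputs.

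**Injection reactions that prevent guided resection.** Protocol 11 reports one anaphylaxis and one extravasation among 289 injected feasibility subjects. Scaled to 406, that is 406/289 ≈ 1.4 of each. Suppose k such subjects fall among 206 without a shave, at a 10% rate otherwise:
- k = 1: (0.10×205 + 1)/206 = 10.4%
- k = 2: (0.10×204 + 2)/206 = 10.9%

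This shift is under one point.

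**The case against.** **Chromaturia may seldom be recorded as an AE.** This is the strongest objection. Protocol 11 and 11.2 describe urine discoloration in Phase 1, yet 11.2 says no LUM015-related AEs were observed there. Protocol 4.6.1 names a single AE for feasibility Phases A and B, a discoloration at the injection site, although 55 of those 60 patients were injected (5 of the 15 in Phase A received no LUM015). The AE definition also requires an undesirable sign. If b is 2% to 5%, power in the illustration is 74% to 67%, a modest loss from 79%. This stands as a limit on size. It does not remove the point, because Table 4 now lists chromaturia as a Frequent AE and nothing excludes it from the comparison.

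**A reader might infer that a null result is likely whatever the shaves do.** The documents do not support that. It requires chromaturia to be recorded in a large share of subjects, and they give no such rate.

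**A reader might also infer serious bias from reactions that stop the procedure.** The feasibility counts suggest only one or two subjects of each type. Protocol 6.2.9 excludes patients with a history of contrast allergy. Extravasation removes a patient from the efficacy cohort, but no section says that it prevents guided resection.

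**Other tables give part of the information.** SAP 4.8 plans AEs by system organ class, preferred term, severity and relatedness, and SAP 4.11 adds subject listings. SAP 4.7 also promises specific AEs in prespecified groups. However, those groups are not named, and none of the tables is specified by shave status.

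**The comparison is one of many secondary endpoints, with no stated level or success rule.** This is true and limits the weight of the point. It is nonetheless a formal test whose event definition does not fit the exposure being compared.

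**Conclusion.** The point holds as a defect in how the event is defined. Followed as written, the comparison includes events that start before the shave and cannot result from it, and a shave-related excess shrinks by (1−b). That factor assumes background events that are equal in the two groups and independent of other AEs.

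The size cannot be settled from the documents. Under 20% vs 10% and 200 vs 206 subjects, the power loss runs from about 5 points at b = 2% to about 63 points at b = 50%. All of these inputs are assumptions, and the recording history in the earlier studies is compatible with the low end. The directional bias from interrupted procedures is probably minor. The SAP should be changed because the change is cheap and the present wording leaves the result hard to interpret.

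**What to change.** In SAP 4.7, 4.8 and endpoint x, and in protocol endpoint h:

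1. Define the tested comparison as the percent of subjects with at least one AE with onset after SOC completion.
2. From that comparison, exclude by a fixed list of preferred terms the Table 4 LUM015 events (chromaturia, extravasation, anaphylaxis/hypersensitivity), whatever their attribution. The onset rule alone is not enough, because urine discoloration took 12 to 24 hours to resolve in most Phase 1 patients and could first be noted after surgery.
3. Do not use attribution as the filter. Protocol 12.1.6 relates events to the study treatment as a whole, the tables split only drug and device, and neither has a category for the extra resection. The assessor may also know whether a shave was taken.
4. Show AEs by preferred term for each shave group, and name shave status among the prespecified groups in SAP 4.7.
5. State whether chromaturia is to be recorded as an AE.
6. Keep the all-AE comparison as descriptive output, so that no event disappears from view.

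The cost is a few SAP sentences (with matching protocol wording), one derived flag and one table, with no new visits or assessments. Same-day events without an onset time need a convention. AEs of the standard lumpectomy, common to both groups, will remain and still dilute the contrast to some degree.
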